3. STUDY RATIONALE AND OBJECTIVES

3.1. Rationale

The rationale for this study is to assess safety and efficacy of A-101 Solution 40% when applied to up to 4 DPN Target Lesions in subjects with Fitzpatrick Skin Type 5 or 6.

Aclaris recently completed three phase clinical studies (301, 302, and 303) that demonstrated that A-101 40% Solution is both safe and effective in treating subjects with seborrheic keratosis lesions on the face, trunk and extremities. Based on this data and the classification of DPN lesions as a clinical variant of seborrheic keratosis, a study of A-101 in darker skin type subjects with DPN lesions is warranted.

3.2. Study Objectives

3.2.1. Primary Objective

The main objective of this study is to evaluate the safety and efficacy of hydrogen peroxide, A-101 Solution 40% for the treatment of DPN lesions on subjects with a Fitzpatrick Skin Type of 5 or 6.

3.2.2. Secondary Objective

The secondary objective of this study is to assess durability of response.

3.2.3. Exploratory Objective

An exploratory objective of this study is to evaluate the subject's assessment of the treatment with A-101 to DPN lesions using a Subject Self-Assessment Scale.

4. STUDY DESIGN

This is a phase 2 open label study with an initial single arm safety cohort evaluating A-101 40% Topical Solution in subjects with DPN lesions. A second cohort will randomize subjects to two different treatment arms to evaluate different treatment schedules using A-101 40% Topical Solution. Refer to Figure 1: A-101-DPN-201 Study Design. Subjects may have up to 4 Target DPN lesions treated. Lesions that are selected for treatment must be on the subject's face or neck. Subjects will be required to complete a total of 8 study visits.

Cohort 1 A-101 40% Solution 12 Subjects Treatment Days 1 and 22

--

[figure not shown]

Figure 1: A-101-DPN-201 Study Design

The protocol defined study visits for cohort 1 are:

- Visit 1 (Day -13 to 0) screening
- Visit 2 (Day 1) enrollment and study medication treatment
- Visit 3 (Day 8) follow up visit
- Visit 4 (Day 22) follow up visit and second application of study medication if DPN target lesions meet criteria for retreatment
- Visit 5 (Day 29) follow up visit
- Visit 6 (Day 50) follow up visit
- Visit 7 (Day 78) follow up visit;
- Visit 8 (Day 106) follow up visit; end of study

The protocol defined study visits for cohort 2 are:

- Visit 1 (Day -13 to 0) screening
- Visit 2 (Day 1) randomization and study medication treatment
- Visit 3 (Day 15) follow up visit and second application of study medication if DPN target lesions meet criteria for retreatment
- Visit 4 (Day 22) follow up visit
- Visit 5 (Day 29) follow up visit and third application of study medication if DPN target lesions meet criteria for retreatment
- Visit 6 (Day 50) follow up visit

- Visit 7 (Day 78) follow up visit;
- Visit 8 (Day 106) follow up visit; end of study

Refer to Section 6 for a complete list of protocol required study assessments.

4.1. Number of Subjects and Study Centers

Approximately 36 evaluable subjects will be enrolled at up to 2 investigational centers in the US.

4.2. Duration of Study

The duration of study participation is anticipated to be a maximum of 127 days per subject. Subjects will have a total of 8 study visits.

The maximum anticipated duration for the study is 18 months.

5. STUDY ENTRY CRITERIA

5.1. Inclusion Criteria

Subjects must meet all of the following criteria to be considered for participation in this study.

1. Provisions of written informed consent for participation in this study.
2. Male or female ≥ 18 years old.
3. Subject has a clinical diagnosis of dermatosis papulosa nigra.
4. Subject has a Fitzpatrick Skin Type of 5 or 6.
5. Subject has up to 4 Target DPN Lesions located on the subject's face or neck that has not been previously treated and meets the requirements as defined below:
 - a. Have a clinically typical appearance
 - b. Diameter that is between 2mm and less than 5mm
 - c. Height that is ≤ 2 mm
 - d. Have a Physician's DPN Lesion Assessment Score of ≥ 2
 - e. Be a discrete lesion
 - f. Not be covered with hair which, in the investigator's opinion, would interfere with the study medication treatment or the study evaluations
 - g. Not be in an intertriginous fold
 - h. Not be on the eyelids
 - i. Not be within 5mm of the orbital rim
 - j. Not be pedunculated.
 - k. Not be inflamed, irritated or excoriated.
6. Subject chemistry and complete blood count results are within normal limits for the central laboratory. If any of the laboratory values are outside normal limits, the treating investigator must assess the value/s as not clinically significant and document this in the patient's source documents.
7. Woman of childbearing potential must have a negative urine pregnancy test within 14 days of the first application of study drug and agree to use an active method of birth control for the duration of the study
8. Subject is non-pregnant and non-lactating.
9. Subject is in good general health and free of any known disease state or physical condition which, in the investigator's opinion, might impair the evaluation of any Target DPN Lesions or which exposes the subject to an unacceptable risk by study participation.

10. Subject is willing and able to follow all study instructions and to attend all study visits.

5.2. Exclusion Criteria

Subjects are excluded from this study if any 1 or more of the following criteria is met:

1. Subject has clinically atypical and /or rapidly growing DPN lesion.
2. Subject has current systemic malignancy.
3. Subject has a history of hypertrophic scars or keloids
4. Subject has a history of post inflammatory hyperpigmentation lasting longer than 1 year.
5. Subject has used any of the following systemic therapies within the specified period prior to Visit 1:
 - Retinoids; 180 days
 - Corticosteroids; 28 days
 - Antimetabolites (e.g., methotrexate); 28 days
6. Subject has used any of the following topical therapies within the specified period prior to Visit 1 on, or in a proximity to any Target DPN Lesion, that in the investigator's opinion interferes with the study medication treatment or the study assessments:
 - LASER, light or other energy-based therapy (e.g., intense pulsed light [IPL], photodynamic therapy [PDT]; 180 days
 - Liquid nitrogen, electrodesiccation, curettage, imiquimod, 5-fluorouracil (5FU), or ingenol mebutate; 60 days
 - Retinoids; 28 days
 - Microdermabrasion or superficial chemical peels; 14 days
 - Corticosteroids or antibiotics; 14 days.
7. Subject currently has or has had any of the following within the specified period prior to Visit 1 on or in a proximity to any Target DPN Lesion that, in the investigator's opinion, interferes with the study medication treatment or the study assessments:
 - Cutaneous malignancy; 180 days
 - Sunburn; currently
 - Pre-malignancy (e.g. actinic keratosis); currently
 - Body art (e.g. tattoos, piercing, etc.); currently
 - Excessive tan. The use of self-tanning lotions/sprays are prohibited.
8. Subject has a history of sensitivity to any of the ingredients in the study medications.
9. Subject has any current skin disease (e.g. psoriasis, atopic dermatitis, eczema, sun damage), or condition (e.g. sunburn, excessive hair, open wounds) that, in the opinion of the investigator, might put the subject at undue risk by study participation or interfere with the study conduct or evaluations.
10. Participation in another therapeutic investigational drug trial in which administration of an investigational study medication occurred with 30 days prior to Visit 1.

5.3. Removal of Patients from Study Therapy

A subject may be removed from the study therapy for a variety of reasons, including:

- Unacceptable adverse event

- Subject unwilling or refusal to continue with the protocol defined study visits and/or consent withdrawal for study participation
- Change in compliance with an inclusion/exclusion criteria
- Pregnancy
- General or specific changes in the subject's condition that render the subject unacceptable for further treatment in this study in the judgement of the investigator.

If a subject is to be withdrawn from the study, the Aclaris Therapeutics, Inc. study monitor or designee must be informed of the decision to remove the subject from the study.

The study may be discontinued at the discretion of Aclaris Therapeutics, Inc. Some examples of reasons for discontinuation are the occurrence of the following:

- Increased frequency, severity or duration of known AEs
- Medical, regulatory or ethical reasons affecting the continued performance of the study
- Difficulties in the recruitment of subjects.

5.4. Withdrawal Procedures

If a subject withdraws from the study prior to Visit 8, the reason for and the date of withdrawal from the study must be recorded on the eCRF. If the reason for withdrawal is an adverse event or a clinically significant abnormal laboratory test result, monitoring of the subject will continue until the event has resolved or stabilized, until the patient is referred to the care of a local health care professional, or until a determination of a cause unrelated to the study drug or study procedure is made.

5.5. Subject Replacement

If a subject is enrolled to the study but does not receive a dose of study drug, then the subject will be replaced.

5.6. Subject Identifier (SI)

The investigator or designee will assign a unique five-digit subject identifier (SI) to each subject at Visit 1.

The SI format will be NN-NNN where the first 2 digits are the investigational center site number (using leading zeroes, as appropriate). The final 3 digits are the subject number and must be assigned in ascending numerical order, without omitting or repeating any number, starting with 001 at each investigational center. For example, the SI for the second subject that signs an informed consent at site number 04 would be 04-002.

The subject will be identified using the SI in all study documentation for the duration of the study.

6. STUDY PROCEDURES

The schedule of study activities (including assessments, tests, exams, disease assessments, and study drug administration) beginning with screening and continuing through the end of study are outlined in Table 2. A written, signed informed consent form (ICF) must be obtained from each subject prior to performing any study related procedure (*i.e.*, vital signs, clinical laboratory sampling, urine pregnancy test or photography).

Table 2: Study Procedures for Cohort 1 Subjects

Visit	V1 Screening	V2	V3	V4	V5	V6	V7	V8
Treatment Day	-13 to 0	1	8	22	29	50	78	106
Treatment Window	N/A	N/A	+ 7 days	+ 4 days	+7 days	± 7days	± 7 days	± 7 days
Study Procedures								
Informed Consent	X							
Inclusion Criteria/Exclusion Criteria	X	X ¹						
Subject Identifier	X ²							
Medical history/demographics	X							
Fitzpatrick Skin Type Assessment	X ³							
Vital Signs	X	X ⁴		X				X
Prior Medications/Therapies	X ⁵							
Clinical Chemistry and CBC ⁶	X							X
Urine Pregnancy Test ⁷	X	X						X
Target Lesion Identification ⁸	X							
Physician's DPN Lesion Assessment ⁹	X	X		X		X	X	X
Subject Self-Assessment Scale ¹⁰	X	X		X		X	X	X
Lesion Dimensions ¹¹	X	X		X		X	X	X
Standardized Photography ¹²	X	X		X		X	X	X
Subject Enrollment		X ¹³						
Local Skin Reactions		X ¹⁴	X	X ¹⁴	X	X	X	X
Study Medication Application		X ¹⁵		X ¹⁵				
Wound Care ¹⁶		X		X				
Subject Instructions	X	X	X	X	X	X	X	X
Concomitant therapies ¹⁷		X	X	X	X	X	X	X
Adverse Events ¹⁸		X	X	X	X	X		

¹Subject inclusion/exclusion criteria will be re-assessed prior to study enrollment during Visit 2.

²Investigational sites will assign a unique five-digit subject identifier to each subject at Visit 1. This subject identifier will be used in all study documentation for the duration of the study.

³Each subject's skin must be assessed during Visit 1 using the Fitzpatrick Skin Type Assessment. Refer to Section 9.5.1 for the scale.

⁴Vital signs [including temperature, pulse, respiratory rate, blood pressure, and weight (Visit 1 only)] will be measured by a qualified staff member at Visit 1, Visit 2 prior to study enrollment, and at Visit 8.

⁵Prior medications/therapies will be collected for a time-period of 13 days prior to Visit 2. Refer to Section 7.7 for a list of permitted and restricted concomitant medications.

⁶A complete blood count (including hematocrit, hemoglobin, platelet count, red blood cell count, white blood cell count and differential (absolute and %) including basophils, eosinophils, lymphocytes, monocytes and neutrophils and a clinical chemistry panel including albumin, alkaline phosphatase, alanine aminotransferase (ALT), aspartate aminotransferase (AST), blood urea nitrogen (BUN), bicarbonate, calcium, chloride, creatinine, glucose, lactate dehydrogenase (LDH), phosphorus, potassium, sodium, total bilirubin, total protein, and uric acid.

⁷Woman of child bearing potential will be required to have a urine pregnancy test at Visit 1, at Visit 2 prior to enrollment and at Visit 8.

⁸The treating investigator will identify up to 4 Target DPN Lesions. Each lesion that is identified to be treated must be in an inconspicuous area.

⁹The investigator will assess each DPN target lesion based on a 4- point Physician's DPN Lesion Assessment Scale. In order to be eligible for enrollment at Visit 2, the subject must have at least one DPN lesion that is between 2mm and 5 mm in diameter. At Visit 2 and if applicable at Visit 4, the investigator must assess each DPN lesion that is to be treated prior to application of the study medication.

¹⁰Subjects will use a Subject Self-Assessment Scale to assess each Target DPN Lesion at Screening Visit 1, at Visit 2 prior to application of the study medication, at Visit 4 (prior to study medication, if applicable), at Visit 6, Visit 7 and Visit 8.

¹¹The investigator will measure the diameter and thickness of each identified Target DPN Lesions at Visit 1 and prior to enrollment. At Visit 2. At Visit 4 prior to retreatment (if applicable, at Visit 6, Visit 7 and at Visit 8 the investigator will only measure the diameter of each Target DPN Lesion.

¹²At Visits 1, Visit 2 (prior to study medication application), Visit 4 prior to study medication application if applicable, Visit 6, Visit 7, and at Visit 8, a qualified investigational center staff member will take a photograph of each DPN lesion that has been treated using the Aclaris supplied camera. All photographs will be sent to a central imaging laboratory.

¹³Subjects will be enrolled to the study at Visit 2 prior to application of study medication. Investigational study staff will re-confirm subject eligibility prior to study enrollment.

¹⁴Both the investigator and the subject will assess each Target DPN Lesion for symptoms associated with irritation. At Visit 2 and Visit 4, the investigator will assess the Target DPN Lesions prior to application of the study medication and 20 (\pm 4) minutes after treatment with the study medication. At Visit 2 and Visit 4, the subject will assess the Target DPN Lesions prior to application of the study medication and 10 (\pm 4) minutes after the treatment of the study medication.

¹⁵A-101 study medication will be applied by the treating physician. All Target DPN Lesions will be treated with study medication following enrollment at Visit 2. If a Target DPN Lesion meets the criteria for re-treatment as defined in Section 7.5, the lesion will be re-treated at Visit 4. Following application of study medication, subjects must NOT wash/submerge the Target DPN Lesions for at least 6 hours and they must NOT apply any topical products to the Target DPN Lesions for at least 6 hours.

¹⁶All subjects will be required to apply Aquaphor to all Target DPN Lesions the morning after study medication application. Sites will be provided supplies of Aquaphor by the Sponsor.

¹⁷All concomitant therapies including (topical and oral) prescription medications, over the counter medications and natural supplements and non-drug therapies including chiropractic, physical therapy, and energy-based therapy must be documented in the subject CRF. Subjects must not apply any topical products (e.g. moisturizers, sunscreen, etc.) to their Target Lesions within 12 hours prior to any study visit.

¹⁸The reporting period for Serious Adverse Events (SAEs) begins when the subject signs the informed consent. Refer to Section 10 for instructions on the reporting of SAEs. Non-serious clinical adverse events will be collected following the application of the study medication at Visit 2. Non-serious adverse events that occur between the time of consent and study medication application will be documented as medical history. All safety reporting (AEs and SAEs) will conclude at Visit 5 (approximately 21 days after last study medication application) except for clinical adverse events related to local skin reactions. These events will be collected through V8.

Table 3: Study Procedures for Cohort 2 Subjects

Visit	V1 Screening	V2	V3	V4	V5	V6	V7	V8
Treatment Day	-13 to 0	1	15	22	29	50	78	106
Treatment Window	N/A	N/A	+ 4 days	+ 2 days	+4 days	± 7days	± 7 days	± 7 days
Study Procedures								
Informed Consent	X							
Inclusion Criteria/Exclusion Criteria	X	X ¹						
Subject Identifier	X ²							
Medical history/demographics	X							
Fitzpatrick Skin Type Assessment	X ³							
Vital Signs	X	X ⁴						X
Prior Medications/Therapies	X ⁵							
Clinical Chemistry and CBC ⁶	X							X
Urine Pregnancy Test ⁷	X	X						X
Target Lesion Identification ⁸	X							
Physician's DPN Lesion Assessment ⁹	X	X	X	X	X	X	X	X
Subject Self-Assessment Scale ¹⁰	X	X	X	X	X	X	X	X
Lesion Dimensions ¹¹	X	X	X	X	X	X	X	X
Standardized Photography ¹²	X	X	X	X	X	X	X	X
Subject Randomization		X ¹³						
Local Skin Reactions		X ¹⁴	X ¹⁴	X	X ¹⁴	X	X	X
Study Medication Application		X ¹⁵	X ¹⁵		X ¹⁵			
Wound Care ¹⁶		X	X		X			
Subject Instructions	X	X	X	X	X	X	X	X
Concomitant therapies ¹⁷		X	X	X	X	X	X	X
Adverse Events ¹⁸		X	X	X	X	X		

¹Subject inclusion/exclusion criteria will be re-assessed prior to study enrollment during Visit 2.

²Investigational sites will assign a unique five-digit subject identifier to each subject at Visit 1. This subject identifier will be used in all study documentation for the duration of the study.

³Each subject's skin must be assessed during Visit 1 using the Fitzpatrick Skin Type Assessment. Refer to Section 9.5.1 for the scale.

⁴Vital signs [including temperature, pulse, respiratory rate, blood pressure, and weight (Visit 1 only)] will be measured by a qualified staff member at Visit 1, Visit 2 prior to study enrollment, and at Visit 8.

⁵Prior medications/therapies will be collected for a time-period of 13 days prior to Visit 2. Refer to Section 7.7 for a list of permitted and restricted concomitant medications.

⁶A complete blood count (including hematocrit, hemoglobin, platelet count, red blood cell count, white blood cell count and differential (absolute and %) including basophils, eosinophils, lymphocytes, monocytes and neutrophils and a clinical chemistry panel including albumin, alkaline phosphatase, alanine aminotransferase (ALT), aspartate aminotransferase (AST), blood urea nitrogen (BUN), bicarbonate, calcium, chloride, creatinine, glucose, lactate dehydrogenase (LDH), phosphorus, potassium, sodium, total bilirubin, total protein, and uric acid.

⁷Woman of child bearing potential will be required to have a urine pregnancy test at Visit 1, at Visit 2 prior to enrollment and at Visit 8.

⁸The treating investigator will identify up to 4 Target DPN Lesions.

⁹The investigator will assess each DPN target lesion based on a 4-point Physician's DPN Lesion Assessment Scale. In order to be eligible for enrollment at Visit 2, the subject must have at least one DPN lesion that is between 2mm and 5 mm in diameter. The investigator must assess each DPN lesion that is to be treated prior to application of the study medication at Visit 2, if applicable at Visit 3 and Visit 5.

¹⁰Subjects will use a Subject Self-Assessment Scale to assess each Target DPN Lesion at Screening Visit 1, Visit 2 (prior to application of the study medication), Visit 3 (prior to study medication, if applicable), Visit 4, Visit 5 (prior to study medication, if applicable), Visit 6, Visit 7 and Visit 8.

¹¹The investigator will measure the diameter and thickness of each identified Target DPN Lesions at Visit 1 and prior to enrollment. At Visit 2. At Visit 3 (prior to treatment, if applicable), Visit 4, Visit 5 (prior to retreatment if applicable), Visit 6, Visit 7 and Visit 8 the investigator will only measure the diameter of each Target DPN Lesion.

¹²At Visits 1, Visit 2 (prior to study medication application) Visit 3 (prior to study medication application, if applicable), Visit 4, Visit 5 (prior to study medication application if applicable), Visit 6, Visit 7, and Visit 8, a qualified investigational center staff member will take a photograph of each DPN lesion that has been treated using the Aclaris supplied camera. All photographs will be sent to a central imaging laboratory.

¹³Subjects will be enrolled to the study at Visit 2 prior to application of study medication. Investigational study staff will re-confirm subject eligibility prior to study enrollment.

¹⁴Both the investigator and the subject will assess each Target DPN Lesion for symptoms associated with irritation. At Visit 2, Visit 3 and Visit 5, the investigator will assess the Target DPN Lesions prior to application of the study medication and 20 (\pm 4) minutes after treatment with the study medication, if applicable. At Visit 2, Visit 3, and Visit 5, the subject will assess the Target DPN Lesions prior to application of the study medication and 10 (\pm 4) minutes after the treatment of the study medication, if applicable.

¹⁵A-101 study medication will be applied by the treating physician. All Target DPN Lesions will be treated with study medication following enrollment at Visit 2. Subjects randomized to ARM B will be required to have their Target DPN Lesions medically abraded prior to treatment with A-101 study medication. If a Target DPN Lesion meets the criteria for re-treatment as defined in Section 7.5, the lesion will be re-treated at Visit 3, and Visit 5. Following application of study medication, subjects must NOT wash/submerge the Target DPN Lesions for at least 6 hours and they must NOT apply any topical products to the Target DPN Lesions for at least 6 hours.

¹⁶All subjects will be required to apply Aquaphor to all Target DPN Lesions the morning after study medication application. Sites will be provided supplies of Aquaphor by the Sponsor.

¹⁷All concomitant therapies including (topical and oral) prescription medications, over the counter medications and natural supplements and non-drug therapies including chiropractic, physical therapy, and energy-based therapy must be documented in the subject CRF. Subjects must not apply any topical products (e.g. moisturizers, sunscreen, etc.) to their Target Lesions within 12 hours prior to any study visit.

¹⁸The reporting period for Serious Adverse Events (SAEs) begins when the subject signs the informed consent. Refer to Section 10 for instructions on the reporting of SAEs. Non-serious clinical adverse events will be collected following the application of the study medication at Visit 2. Non-serious adverse events that occur between the time of consent and study medication application will be documented as medical history. All safety reporting (AEs and SAEs) will conclude at Visit 5 (approximately 21 days after last study medication application) except for clinical adverse events related to local skin reactions. These events will be collected through V8.

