7.5.2. Applying Study Medication to the Face

To apply the study medication to Target Lesions on the **FACE** the staff member will follow these treatment instructions:

- Do not apply the study medications to eyes, mouth, mucous membranes, open wounds
- Do not apply the study medication to the eyelids or within 5 mm of the orbital rim
- If, in the investigator's opinion it is needed to ensure no study medication enters the eye:
 - Position the subject in the supine position with the head slightly elevated and angled such that any excess study medication will flow away from the eye.
 - Aclaris Therapeutics will supply sites supplies of white petrolatum (100%) United States Pharmacopeia (USP) that is to be applied along the orbital rim and at the medial and lateral canthi; gently stretch the periorbital skin between the thumb and forefinger at the time of petrolatum application to distend any periorbital rhytides (e.g., "crow's feet") and ensure full coverage of the skin at the base of the rhytides to decrease the likelihood of tracking of the study medication towards the eye
 - Have the subject hold an absorbent pad in the appropriate area of the eye to absorb any excess study medication that might track away from the Target Lesion

- Instruct the subject to keep both eyes closed during the entire study medication treatment procedure
- After the subject is properly prepared and positioned, thoroughly cleanse the Target Lesion by firmly rubbing with a swab/wipe wetted with 70% isopropyl alcohol
- **Subjects randomized to ARM B of cohort 2 will have their DPN lesions medically abraded prior to the application of the A-101 study medication.
- Using firm pressure, while avoiding squeezing the applicator barrel, apply one drop of study medication onto the DPN lesion and then move applicator around in a circular motion to fully saturate the lesion. Using the smaller Q-tip applicator that is supplied massage the A-101 study medication into the DPN lesion for approximately 15 seconds.
- Minimize exposure to the surrounding normal skin
- During the treatment process remove excess study medication from the surrounding skin using a clean absorbent wipe
- Ensure the DPN Target Lesion is wet with study medication at the end of the ~15 second application
- Allow the DPN Target Lesion to remain undisturbed for ~60 seconds
- After ~60 seconds repeat the ~15 second application process

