Any CR abnormality discovered prior to the first study medication treatment should be reported as medical history, not as an AE.

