10.1.3. Adverse event reporting period

The investigator must start reporting non-serious AEs starting with the subject’s first study medication treatment continuing until Visit 6. Non-serious adverse events that occur between the time the subject was consent and the first application of study medication will be reported as medical history.

Reporting for SAEs begins after the subject signs the informed consent and continues until Visit 6 (regardless of relationship to study medication). If a subject experiences a SAE after Visit 6 that is deemed to be related to study medication, the investigator must report this to the Sponsor using the study specific SAE report form.

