¹⁸ The reporting period for Serious Adverse Events (SAEs) begins when the subject signs the informed consent. Refer to Section 10 for instructions on the reporting of SAEs. Non-serious clinical adverse events will be collected following the application of the study medication at Visit 2. Non-serious adverse events that occur between the time of consent and study medication application will be documented as medical history. All safety reporting (AEs and SAEs) will conclude at Visit 5 (approximately 21 days after last study medication application) except for clinical adverse events related to local skin reactions. These events will be collected through V8.

Page **13** of **26** Date: 19-February-2019

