2.4.3.2 Adverse Events

Non-serious AEs will be recorded starting with the subject's first study medication treatment at Visit 2 and continuing through Visit 6. All SAEs regardless of relationship to study medication will be collected and reported from the time the Informed Consent is signed through Visit 6.

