3.7.3 Adverse Events

All subjects will be assessed regularly for the potential occurrence of adverse events (AEs) from the date of informed consent to Visit 6. The incidence of treatment-emergent AEs (TEAEs) will be defined for new or worsening events from the first study treatment until 30

days after the last study treatment. Summaries will be conducted using MedDRA (version 21.1), by System Organ Class (SOC) and Preferred Term (PT).

An overview of adverse events for the ITT analysis set will be provided, summarizing the incidence of the following:

- Count of TEAEs;
- Subjects with TEAEs;
- Count of Treatment-emergent serious AEs (TESAE);
- Subjects with TESAE;
- TEAE by maximum severity;
- TESAE by maximum severity;
- Subjects with TEAEs that lead to discontinuation of study;
- Subjects with TESAEs that lead to discontinuation of study;
- Subjects with Related TEAEs;
- Subjects with Related TESAEs.

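### In Cohort 2, non-serious adverse events are recorded only from the first A-101 application, so those starting between Arm B's first abrasion and that application become medical history.

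*Protocol*

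**What the plan says.** **When recording starts.** Table 3 (Cohort 2), footnote 18, states: "Non-serious adverse events that occur between the time of consent and study medication application will be documented as medical history". Protocol 10.1.3 repeats the rule: "Non-serious adverse events that occur between the time the subject was consent and the first application of study medication will be reported as medical history". Protocol 10.1.1 adds, for clinically relevant findings: "Any CR abnormality discovered prior to the first study medication treatment should be reported as medical history, not as an AE". The SAP carries this over. Its Table 2, footnote 18, says "Non-serious clinical adverse events will be collected following the application of the study medication at Visit 2", and SAP 2.4.3.2 says "Non-serious AEs will be recorded starting with" the first study medication treatment at Visit 2. Serious events are collected from consent.

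**When abrasion happens.** Table 3, footnote 15: "Subjects randomized to ARM B will be required to have their Target DPN Lesions medically abraded prior to treatment with A-101 study medication". Section 7.5.2 (face) says that subjects in "ARM B of cohort 2 will have their DPN lesions medically abraded prior to the application of the A-101 study medication", and 7.5.3 (neck) says the same. Both place abrasion after alcohol cleansing and before the drug.

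**What is analysed.** In SAP 3.7.3 the incidence of treatment-emergent events (TEAEs) "will be defined for new or worsening events from the first study treatment" until 30 days after the last. The same paragraph also says that subjects are assessed for AEs from consent to Visit 6. SAP 3.1 presents summaries by arm, and the protocol synopsis makes all safety summaries descriptive.

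**The concern.** Footnote 18 has the same wording in the Cohort 1 and Cohort 2 tables. In Cohort 1, nothing but alcohol cleansing precedes the drug, so starting the AE clock at application loses little. Amendment 1 added Cohort 2, in which Arm B has an abrasive procedure before the drug, and the clock was not moved.

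Abrasion is the only difference between the two randomised arms, and safety is part of the primary objective. An immediate, non-serious reaction to the first abrasion is the kind of event the comparison should show. Under the written rule it goes into a baseline table instead. The first abrasion is also the only one that every Arm B subject is due to receive, since those at Visits 3 and 5 depend on retreatment criteria. SAP section 4 shortens the efficacy reporting but keeps the safety reporting in full, so these tables carry much of the report.

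**Working it through.** The plan states no AE rate or event count to reproduce. The check sets the order of procedures against the recording rules.

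**Step 1: classify a non-serious event in Cohort 2 by its onset.**

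| Onset | Arm A exposure | Arm B exposure | Recorded as |
|---|---|---|---|
| Visit 2, randomisation to first application | alcohol cleansing | alcohol cleansing, then abrasion | medical history (footnote 18; 10.1.1; 10.1.3; SAP 2.4.3.2) |
| Visit 2, after first application | drug | abrasion and drug | AE |
| Earlier onset, worse after application | drug | abrasion and drug | AE (10.1.1 covers worsening; so does SAP 3.7.3) |
| Around abrasion at Visit 3 or 5 | not applicable | repeat abrasion | AE |

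Only the first row is lost. It contains abrasion in Arm B and cleansing alone in Arm A.

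**Step 2: is the event still a TEAE under the SAP?** SAP 3.7.3 counts from a first study treatment that it does not define.

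- *For the drug-application reading:* SAP 3.5 sets medication before the first study treatment against medication on or after the first application, as if the two were the same moment. SAP 3.7.1 works from application dates. Footnote 15 places abrasion before treatment.
- *For the wider reading:* Protocol 7.5.2 and 7.5.3 list cleansing and abrasion among the treatment instructions, and 7.2 defines Arm B as a treatment arm that includes abrasion.

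The drug-application reading is better supported, and on it the event is not a TEAE. On the wider reading it could be a TEAE, but the protocol would still have filed it as history and there would be no AE record to count.

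**Step 3: do local skin reactions (LSRs) fill the gap?** Only in part. Protocol 9.1 has the subject grade stinging/burning and itch 10 minutes after treatment. The investigator grades erythema, edema, scaling/dryness and vesicles/bullae at 20 minutes. Pain as such, bleeding and fainting are not LSR items, and erosion and ulceration are not in the 20-minute check.

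**Step 4: scale.** The inputs are 24 Cohort 2 subjects (synopsis) and 1:2 allocation (Protocol 7.2).

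- Arm A = 24 × 1/3 = 8. Arm B = 24 × 2/3 = 16, with at most 16 × 4 = 64 first-abraded lesions.
- One Arm B subject is 1/16 = 6.25 percentage points of that arm's subject incidence, if the subject has no other AE.
- Let p be the chance that an Arm B subject has a non-serious event with onset in the interval. The documents give no p, so the values below are assumptions. Expected subjects = 16p. Chance of at least one = 1 − (1 − p)^16, taking subjects as independent.

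| Assumed p | 16p | 1 − (1 − p)^16 |
|---|---|---|
| 5% | 0.8 | 1 − 0.95^16 = 0.56 |
| 10% | 1.6 | 1 − 0.90^16 = 0.81 |
| 25% | 4.0 | 1 − 0.75^16 = 0.99 |

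**The case against.** The strongest reply is that the interval is short and much is caught elsewhere. Application follows abrasion directly in the instructions. Infection, pigment change or scarring would appear later and be collected, and an event that worsens after application qualifies as an AE. LSRs are graded at every later visit, with erosion, crusting, ulceration and scarring on the full list. In addition, 10.1.1 treats worsening of Target Lesion assessments as an AE only when study medication is interrupted or stopped, or therapy is needed. Some local effects would therefore not be AEs under any start date. All of this stands, and it narrows the point to events with onset before the first application.

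A second reply is that SAP 3.7.3 has AEs assessed from consent. That sentence conflicts with SAP 2.4.3.2 and with the protocol, which governs what sites record. It shows an inconsistency but does not cure the gap.

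Four stronger readings are tempting but not supported:

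- *All non-serious harm from the first abrasion is lost.* Only events with onset before application are.
- *The loss is confined to Arm B.* Both arms have lesions rubbed with alcohol in the interval, so the loss is unequal rather than exclusive to one arm.
- *Serious events drop out.* They are reported from consent. Whether one on the same day, before application, counts as treatment-emergent is unclear, because the SAP does not say whether dates or clock times decide.
- *Anaesthetics or haemostatics used for abrasion are misclassified.* The documents mention neither for abrasion, and Protocol 7.7.2 counts any therapy from Visit 1 as concomitant.

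**Conclusion.** The point holds in this limited form. By stated rule, non-serious events with onset between the first abrasion and the first A-101 application at Visit 2 are medical history and not AE records. On the better-supported reading of the SAP they are not TEAEs either. The loss falls mainly on Arm B and tends to make abrasion look safer in its immediate effects.

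The size is unknown. It depends on an event rate and an interval length that the documents do not give, so the assumed risks show scale only and are not evidence that events will occur. The arm size of 16 assumes that the planned 24 are randomised exactly 1:2.

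A reader might infer that a treatment test is biased or that the Arm B AE table must show zero abrasion events. Neither follows. Safety is descriptive, and later-onset events, worsening events and events from repeat abrasions would appear. This is a should-fix: a real, directional gap on the randomised question, but a narrow one.

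**What to change.** For both Cohort 2 arms, start non-serious AE collection and the treatment-emergent period at one common point. That point is either randomisation at Visit 2 or the start of the first treatment procedure (abrasion or application, whichever comes first). Limit the medical-history rule to events before it.

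- **Protocol:** Table 3 footnote 18, 10.1.1 and 10.1.3. Also change the same anchor in 9.2 and 9.3. No scheduled vital sign or blood sample falls in the interval, so that edit is for consistency and for unscheduled findings.
- **SAP:** Table 2 footnote 18, 2.4.3.2, 2.4.3.4 and 3.7.3. Reconcile the assessment period from consent in 3.7.3 with 2.4.3.2, and define the first study treatment once. Use the same anchor in 3.5.

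The cost is wording edits in several sections of two documents and a few extra AE records from the minutes between randomisation and application. No visit, procedure or assessment is added.
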